9.2.5 Microbiome Analyses – Exploratory Laboratory Correlative Study #5

9.2.5.1 *Collection of Specimen(s)*

Fecal samples will be collected by patients pre-treatment and post-treatment using standard, at home stool-collection procedures using standardized fecal swab/storage devices.

9.2.5.2 *Handling of Specimens(s)*

Samples will be initially stored frozen at home by patients and returned to the clinical research site at their next study visit and stored at the local site at -80°C.

9.2.5.3 *Shipping of Specimen(s)*

Frozen samples will be batch shipped overnight on dry ice to the CIML. Sites will utilize a web-based specimen system (BSI-Web) to communicate with the CIML. The CIML will coordinate the shipment of samples to Dr. [REDACTED] at Fred Hutch.

9.2.5.4 *Site(s) Performing Correlative Study*

Assays will be performed in collaboration with Dr. [REDACTED] at Fred Hutch or other collaborator.

9.3 Special Studies

9.3.1 *Immunogenicity Testing*

The formation of anti-drug antibodies (ADA) and neutralizing anti-drug antibodies (NADA) to glyco-rhIL-7 (CYT107) will be evaluated in the Safety Run-In/Experimental Arm subjects only, on Cycle 1, Day 1 before the first CYT107 injection and on Cycle 3, Day 1. If positive on Cycle 3, Day 1, immunogenicity testing will be repeated at the end of the study.

9.3.1.1 *Collection of specimen(s)*

Blood draws will be performed by venipuncture on study subjects before, during and at end of treatment.

9.3.1.2 *Handling of specimen(s)*

Plasma will be isolated by the local laboratory and frozen at -80C.

9.3.1.3 *Shipping of Specimen(s)*

Plasma samples will be batch shipped overnight on dry ice to the CIML (Seattle, WA). Sites will utilize a web-based specimen system (BSI-Web) to communicate with the CIML. The CIML will coordinate the shipment of samples to the agreed upon collaborator or vendor.

9.3.1.4 *Site(s) Performing Immunogenicity Testing*

ADA and NADA to glyco-rhIL-7 (CYT107) will be performed by Eurofins Scientific (Vergeze, France) who will perform both ELISA Binding (non-neutralizing) and neutralizing antibody assays according to their Standard Operating Procedure.

9.3.2 *CYT107 Pharmacokinetics*

The pharmacokinetic profile of CYT107 levels will be assessed to determine if Atezolizumab has an effect on CYT107 PK levels. The samples will be collected before CYT107 treatment on Cycle 1, Day 1 and again on Cycle 1, Day 22.

9.3.2.1 *Collection of specimen(s)*

Blood draws will be performed by venipuncture on study subjects before and during study treatment.

Table 9.3.2 Pharmacokinetics timepoints

Cohort	Pharmacokinetic timepoints for CYT107
Safety Run-in subjects	Day 1, Immediate Pre-dose CYT107
Safety Run-in subjects	Day 1, 2 hours (\pm 15 mins) after CYT107 administration is complete
Safety Run-in subjects	Day 1, 4 hours (\pm 15 mins) after CYT107 administration is complete
Safety Run-in subjects	Day 1, 6 hours (\pm 15 mins) after CYT107 administration is complete
Safety Run-in subjects	Day 22, Immediate Pre-dose CYT107 and Atezolizumab
Safety Run-in subjects	Day 22, 2 hours (\pm 15 mins) after CYT107 administration is complete*
Safety Run-in subjects	Day 22, 4 hours (\pm 15 mins) after CYT107 administration is complete*
Safety Run-in subjects	Day 22, 6 hours (\pm 15 mins) after CYT107 administration is complete*

**Blood draws are timed after CYT107 administration is complete, not completion of Atezolizumab infusion.*

9.3.2.2 *Handling of Specimens(s)*

Plasma will be isolated by the local laboratory and frozen at -80°C.

9.3.2.3 *Shipping of Specimen(s)*

Plasma samples will be batch shipped overnight on dry ice to the CIML (Seattle, WA). Sites will utilize a web-based specimen system (BSI-Web) to communicate with the CIML. The CIML will coordinate the shipment of samples to the agreed upon collaborator or vendor.

9.3.2.4 *Site(s) Performing Pharmacokinetics Testing*

PK of glyco-rhIL-7 (CYT107) will be performed by Eurofins Scientific (Vergeze, France) who will perform assays according to their Standard Operating Procedures.

10. STUDY CALENDAR

Baseline evaluations are to be conducted within 14 days before the initiation of study treatment. Scans and x-rays must be done <4 weeks (28 days) before the initiation of study treatment. In the event that the patient's condition is deteriorating, laboratory evaluations should be repeated within 48 hours before the initiation of the next cycle of therapy. Patients receiving atezolizumab will be assessed for pulmonary signs and symptoms throughout the study.

SAFETY RUN-IN/EXPERIMENTAL ARM																				
Treatment Cycle		Cycle 1				Cycle 2				Cycle 3				Subsequent Cycle (Repeat up to 2 year)			End of Tx	Post-Treatment Follow-up		
Weeks	Screening visit	Wk1 ^a	Wk2	Wk3	Wk4	Wk5	Wk6	Wk7	Wk8	Wk9	Wk10	Wk11	Wk12	Wk13	At time of D/C ± 5 days	Safety FU	Disease Assessment ^f	Survival FU		
	Within 14 days	Day 1 ± 2	Day 8 ± 2	Day 15 ± 2	Day 22 ± 2	Day 1 ± 2	Day 8 ± 2	Day 15 ± 2	Day 1 ± 2	Day 8 ± 2	Day 15 ± 2	Day 1 ± 2	Day 8 ± 2	Day 15 ± 2		30 days ± 5 post DC	Every 12 ± 1 weeks	Every 12 ± 1 weeks		
Atezolizumab		A			A			A			A									
CYT107		B	B	B	B															
Administrative procedures																				
Informed consent	X																			
Demographics	X																			
Medical history	X																			
Concurrent meds	X	X-----				-----X				-----X				X	X	X	X			
Clinical Procedures/Assessments																				
Physical exam	X	X				X			X			X			X	X				
Vital signs ^b	X	X	X	X	X	X			X			X			X	X				
Height	X																			
Weight	X	X	X	X	X	X			X			X			X	X				
Adverse event evaluation		X-----				-----X				-----X				X	X	X				
Immune-related AEs evaluation		X-----				-----X				-----X				X	X	X				
Performance status	X	X	X	X	X	X			X			X			X	X				
EKG (as indicated)	X																			
Laboratory Assessments (Safety Labs)																				
CBC w/diff, plt	X	X	X	X	X	X			X			X			X	X				
Serum chemistry ^c	X	X	X	X	X	X			X			X			X	X				
Pregnancy Test (Urine or Serum HCG)	X ^d														X					
Efficacy Measurements																				
Tumor measurements	Within 28 days	Tumor measurements are repeated every 9±1 weeks . Documentation (radiologic) must be provided for patients removed from study for progressive disease.												X		X				
Radiologic evaluation ^k	Within 28 days	Radiologic measurements should be performed every 9 ± 1 weeks .												X		X				

SAFETY RUN-IN/EXPERIMENTAL ARM																				
Treatment Cycle		Cycle 1				Cycle 2				Cycle 3				Subsequent Cycle (Repeat up to 2 year)			End of Tx	Post-Treatment Follow-up		
Weeks	Screening visit	Wk1 ^a	Wk2	Wk3	Wk4	Wk5	Wk6	Wk7	Wk8	Wk9	Wk10	Wk11	Wk12	Wk13	At time of D/C ± 5 days	Safety FU	Disease Assessment ⁱ	Survival FU		
Scheduling Window	Within 14 days	Day 1	Day 8 ± 2	Day 15 ± 2	Day 22 ± 2	Day 1 ± 2	Day 8 ± 2	Day 15 ± 2	Day 1 ± 2	Day 8 ± 2	Day 15 ± 2	Day 1 ± 2	Day 8 ± 2	Day 15 ± 2	30 days ± 5 post DC	Every 12 ± 1 weeks	Every 12 ± 1 weeks			
Tumor Biopsies/Archival Tissue Collection																				
Tumor Biopsy	X ^e													X ^j		X ^j				
Correlative Studies Blood Draws ^h																				
T cell (CD4+ and CD8+) count		X	X ^f	X	X	X ^f			X ^f			X ^f								
Immunophenotyping		X	X			X			X						X					
Multiplex Cytokines		X				X			X						X					
TCR sequencing		X	X			X			X											
ELISPOT		X				X			X											
Kyn/Trp and Arginine		X				X			X						X					
Microbiome	X ^g								X ^g											
PK CYT107 ⁱ			X ^l		X ^l															
Immunogenicity CYT107		X ^m							X ^m						X ^m					

A: Atezolizumab: Dose as assigned; once every 3 weeks, starting Cycle 1, Day 8

B: CYT107: Dose as assigned; Cycle 1, Days 1, 8, 15 and 22; must be administered before atezolizumab on Cycle 1, Day 8

a: For patients receiving CYT107 (Run-In phase or Experimental arm) *only*

b: Vital signs assessment before and after CYT107 injection and/or Atezolizumab infusion is required ([section 5.1.1](#) and [5.1.2](#))

c: Albumin, alkaline phosphatase, total bilirubin, bicarbonate, BUN, calcium, chloride, creatinine, glucose, LDH, phosphorus, potassium, total protein, SGOT [AST], SGPT [ALT], sodium, INR, aPTT.

d: Pregnancy test (women of childbearing potential) must be performed within 72 hours prior to initiation of study treatment.

e: Tumor biopsy tissue (archival or fresh) is required per eligibility criteria [3.1.8](#).

f: To be performed prior to the first 4 doses and the 6th dose of atezolizumab

g: Fecal swab/storage devices and instructions must be given to patient; sample collection to be performed at home by patient and returned to clinical research site at the next study visit (Cycle 1, Day 1 and Cycle 4, Day 1).

h: Correlative Studies Blood draws must be performed prior to study agent(s) administration on a dosing day.

i: Disease assessment per standard of care

j: Post-treatment tumor biopsy will be obtained prior to dosing on Cycle 4, Day 1 *or* at the End of Treatment visit, whichever occurs first.

k: Patients with known CNS metastases must also have a brain MRI imaging at all standard radiologic evaluation timepoints

l: PK (Pharmacokinetics) for CYT107 samples to be drawn on the first 6 patients enrolled in the run-in phase of the study, before the first and fourth administration and at 2hrs, 4 hrs, and 6 hrs after the first and fourth CYT107 administrations

m: Immunogenicity testing (anti-drug antibody testing or ADA testing) will be done on all subjects who receive CYT107. Testing will be done on Cycle 1, Day 1 and on Cycle 3, Day 1. If positive on Cycle 3, Day 1, testing to be repeated at End of Treatment visit.

Baseline evaluations are to be conducted within 14 days before the initiation of study treatment. Scans and x-rays must be done <4 weeks (28 days) before the initiation of study treatment. In the event that the patient's condition is deteriorating, laboratory evaluations should be repeated within 48 hours before the initiation of the next cycle of therapy. Patients receiving atezolizumab will be assessed for pulmonary signs and symptoms throughout the study.

CONTROL ARM																		
Treatment Cycle	Screening visit	Cycle 1			Cycle 2			Cycle 3			Subsequent Cycle (Repeat up to 2 year)			End of Tx	Post-Treatment Follow-up			
		Wk1	Wk2	Wk3	Wk4	Wk5	Wk6	Wk7	Wk8	Wk9	Wk10	Wk11	Wk12		At time of D/C ± 5 days	Safety FU	Disease Assessment ^h	Survival FU
Scheduling Window	Within 14 days	Day 1 ± 2	Day 8 ± 2	Day 15 ± 2	Day 1 ± 2	Day 8 ± 2	Day 15 ± 2	Day 1 ± 2	Day 8 ± 2	Day 15 ± 2	Day 1 ± 2	Day 8 ± 2	Day 15 ± 2		30 days ± 5 post DC	Every 12 ± 1 weeks	Every 12 ± 1 weeks	
Atezolizumab		A			A			A			A							
Administrative procedures																		
Informed consent	X																	
Demographics	X																	
Medical history	X																	
Concurrent meds	X	X-									X			X	X	X	X	X
Clinical Procedures/Assessments																		
Physical exam	X				X			X			X			X	X			
Vital signs ^a	X	X	X	X	X			X			X			X	X			
Height	X																	
Weight	X	X	X	X	X			X			X			X	X			
Adverse event evaluation		X-									X			X	X	X		
Immune-related AEs evaluation		X-									X			X	X	X		
Performance status	X	X	X	X	X			X			X			X	X			
EKG (as indicated)	X																	
Laboratory Assessments (Safety Labs)																		
CBC w/diff, plts	X	X	X	X	X			X			X			X	X			
Serum chemistry ^b	X	X	X	X	X			X			X			X	X			
Pregnancy Test (Urine or Serum HCG)	X ^c													X				
Efficacy Measurements																		
Tumor measurements	Within 28 days	Tumor measurements are repeated every 9±1 weeks . Documentation (radiologic) must be provided for patients removed from study for progressive disease.											X		X			
Radiologic evaluation ^d	Within 28 days	Radiologic measurements should be performed every 9±1 weeks .											X		X			
Tumor Biopsies/Archival Tissue Collection																		
Tumor Biopsy	X ^d										X ⁱ			X ⁱ				

CONTROL ARM																	
Treatment Cycle		Cycle 1			Cycle 2			Cycle 3			Subsequent Cycle (Repeat up to 2 year)			End of Tx	Post-Treatment Follow-up		
	Screening visit	Wk1	Wk2	Wk3	Wk4	Wk5	Wk6	Wk7	Wk8	Wk9	Wk10	Wk11	Wk12	At time of D/C ± 5 days	Safety FU	Disease Assessment ^h	Survival FU
Scheduling Window	Within 14 days	Day 1	Day 8 ± 2	Day 15 ± 2	Day 1 ± 2	Day 8 ± 2	Day 15 ± 2	Day 1 ± 2	Day 8 ± 2	Day 15 ± 2	Day 1 ± 2	Day 8 ± 2	Day 15 ± 2	At time of D/C ± 5 days	30 days ± 5 post DC	Every 12 ± 1 weeks	Every 12 ± 1 weeks
Correlative Studies Blood Draws^g																	
T cell (CD4+ and CD8+) count		X ^e			X ^e			X ^e			X ^e						
Immunophenotyping		X			X			X						X			
Multiplex Cytokines		X			X			X						X			
TCR sequencing		X			X			X									
ELISPOT		X			X			X									
Kyn/Trp and Arginine		X			X			X						X			
Microbiome	X ^f							X ^f									

A: Atezolizumab: Dose as assigned; once every 3 weeks, starting Cycle 1, Day 1

a: Vital signs assessment before and after Atezolizumab infusion is required (section 5.1.1)

b: Albumin, alkaline phosphatase, total bilirubin, bicarbonate, BUN, calcium, chloride, creatinine, glucose, LDH, phosphorus, potassium, total protein, SGOT [AST], SGPT [ALT], sodium, INR, aPTT.

c: Pregnancy test (women of childbearing potential) must be performed within 72 hours prior to initiation of study treatment.

d: Tumor biopsy tissue (archival or fresh) is required per eligibility criteria.

e: To be performed prior to the first 4 doses and the 6th dose of atezolizumab

f: Fecal swab/storage devices and instructions must be given to patient; sample collection to be performed at home by patient and returned to clinical research site at the next study visit (Cycle 1, Day 1 and Cycle 4, Day1).

g: Correlative Studies Blood draws must be performed prior to study agent(s) administration on a dosing day.

h: Disease assessment per standard of care

i: Post-treatment tumor biopsy will be obtained prior to dosing on Cycle 4, Day 1 or at the End of Treatment visit, whichever occurs first.

j: Patients with known CNS metastases must also have a brain MRI imaging at all standard radiologic evaluation timepoints

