Regimens of weekly IL-7 at the 10 μ g/kg level demonstrate an acceptable safety profile with very few grade 3 or 4 adverse events. More than 380 patients have been exposed to CYT107, including 236 patients in 7 phase I/IIa dose escalation studies with CYT107 in oncology, hematopoietic stem cell transplantation (HSCT), human immunodeficiency virus (HIV), hepatitis C virus (HCV) and hepatitis B virus (HBV) infected patients and 2 phase II studies in patients with HIV. CYT107 has been well tolerated [CYT107 Investigator's Brochure]. The most frequent adverse events are:

injection site reactions, lymphadenopathy, pyrexia, rash, and fatigue. A cumulative 819 administrations of CYT107 triggered 555 injection site reactions AE, *i.e.*, 70% of CYT107 administrations led to at least one injection site reaction. The worst grade reported was grade 2 in 159 of 819 administrations (19.4%). No grade 3 or 4 injection site reactions were reported.

Among the 555 injection site reactions related to CYT107:

- 113 (20.3%) were of grade <1
- 283 (51.0%) were of grade 1
- 159 (28.7%) were of grade 2
- No grade 3 or 4 injection site reactions were reported.

Of note, this scoring was performed with reference to the DAIDS 2.0 scale which is more severe than CTCAE scoring.

One true anaphylactic reaction and 4 acute allergic reactions have been reported, strictly in studies with repeated cycles of CYT107. The immunogenicity frequency and the occurrence of NADA (neutralizing antibodies) are higher with the exposure to multiple cycles of CYT107.

Two studies analyzed the pharmacokinetics of CYT107 in patients with HIV-1 with CD4 T-cell counts of 101-400 cells/ μ L and plasma HIV RNA <50 copies/mL while receiving highly active antiretroviral therapy (HAART) for \geq 12 months. Three dose levels of CYT107 were tested sequentially: 10, 20 and 30 μ g/kg. Increasing doses induced a dose response increase in peripheral blood T cells. The increases were nonlinearity above 20 μ g/kg/week in the lymphopenic patients and above 30 μ g/kg/week for the non-lymphopenic patients. The nonlinearity was presumed to be to the administered IL-7 being cleared by binding to an increased number of T cells, *i.e.*, a "Target Mediated Drug Disposition" [CYT107 Investigator's Brochure].

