5. TREATMENT PLAN

This is a phase II trial of atezolizumab (MPDL3280A) plus recombinant human IL-7 (CYT107) in patients with locally advanced or metastatic urothelial carcinoma. The trial follows a randomized, controlled trial design, with an initial 'Safety Run-In' phase designed to evaluate the acute safety profile of the investigational treatment combination.

During the Safety Run-In phase, 6 patients will be assigned to the experimental arm (atezolizumab + CYT107) with staggered enrollment. This will be accomplished with an initial 3 patient enrollment. All adverse events will be assessed by the Toxicity Evaluation Committee. If 0-1 patient experiences a protocol-defined DLT (refer to [Section 5.2](#)) after completion of the 4-week DLT window, an additional 3 patients will be enrolled. Once all 6 patients have completed the 4-week DLT window, the Toxicity Evaluation Committee will again assess all adverse events. If, at any time, 2 or more patients experience a protocol-defined DLT, further enrollment into the trial will be suspended.

If the treatment combination of the experimental arm demonstrates an acceptable safety profile in the Safety Run-In (one or fewer patient experiences a protocol-defined DLT), randomized enrollment into the trial will begin.

Patients will be randomly assigned to either the control arm (atezolizumab monotherapy) or experimental arm (atezolizumab + CYT107) of the trial.

The first 6 subjects enrolled in the run-in phase of the study will have PK sampling done at baseline (prior to CYT107 administration), and at week 4 prior to CYT107 administration and at 2 hours, 4 hours and 6 hours after the fourth CYT107 administration.

Anti-drug antibody testing (ADA testing) will be done on all subjects who receive CYT107. Testing will be done at baseline (prior to CYT107 administration) and at week 8, (1 month after

the last CYT107 administration.) Any subject who develops binding antibodies will be further tested for the presence of anti-CYT107 neutralizing antibodies.

Randomization in the OPEN system may be performed up to 5 business days before initiation of study treatment to allow for clinical site logistics.

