5.1.2 Recombinant Human IL-7 (CYT107)

Patients enrolled in the Safety Run-in phase and patients randomly assigned to the experimental arm of the trial will receive recombinant human IL-7 (CYT107). The patients will receive 10 mcg/kg of IL-7 (CYT107) IM on days 1, 8, 15 and 22 of Cycle 1 only. The CYT107 dose must be administered before atezolizumab on Day 8 of Cycle 1.

For patient with a Body Mass Index (BMI) >30, an adjusted body weight will be used to calculate the final dose the patient will receive. Please refer to [Appendix D](#) for details on the adjusted body weight calculation.

Patients receiving CYT107 will have their vital signs (heart rate, respiratory rate, blood pressure, and temperature) determined within 60 minutes before the first CYT107 injection on day 1, and 2 hours (\pm 15 minutes) after the injection.

On day 8, vital signs will be monitored as described above ([Section 5.1.1](#)) following the guidelines for the first atezolizumab infusion.

On days 15 and 22, vital signs will be determined within 60 minutes before and within 30 minutes after the injection.

Patients will be informed about the possibility of the development of an allergic reaction to CYT107 (hives, bronchospasm, rash, etc.) and instructed to contact their study physician if they develop such symptoms.

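### CYT107-treated patients who leave before Cycle 3 Day 1 have no scheduled post-dose anti-drug antibody sample, so immunogenicity results will be incomplete and may be understated

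*Combined protocol and SAP*

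**What the plan says.** Section 5 (Treatment Plan) sets the population: "Anti-drug antibody testing (ADA testing) will be done on all subjects who receive CYT107". It sets the timing as "Testing will be done at baseline (prior to CYT107 administration) and at week 8, (1 month after" the last CYT107 dose). Footnote m to the experimental-arm table in Section 10 (Study Calendar) names the same population and gives the visits: "Testing will be done on Cycle 1, Day 1 and on Cycle 3, Day 1". It then adds the conditional repeat: "If positive on Cycle 3, Day 1, testing to be repeated at End of Treatment visit".

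Section 9.3.1 has the same two visits and the same condition but places the repeat elsewhere: "If positive on Cycle 3, Day 1, immunogenicity testing will be repeated at the end of the study". Section 9.3.1.1, on specimen collection, says without any condition: "Blood draws will be performed by venipuncture on study subjects before, during and at end of treatment".

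CYT107 is given "IM on days 1, 8, 15 and 22 of Cycle 1 only" (Section 5.1.2).

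**The concern.** The repeat is triggered only by a positive result at Cycle 3 Day 1. A patient who has left by then has no result at that visit, so the trigger cannot fire. The schedule therefore cannot deliver the testing of all recipients that Section 5 and footnote m promise.

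The protocol expects some patients to leave this early. Section 6.2 takes patients off protocol therapy for treatment-related grade 3 or 4 events, with stated exceptions. Sections 5.2.2 and 5.7 provide for run-in patients who leave within the 28-day window because of rapid progression, death, withdrawn consent or a non-dose-limiting event. Most of these will already have received CYT107.

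An antibody result is of particular interest in a patient who stops after a severe hypersensitivity reaction. Without it, any link between antibodies and early stopping cannot be examined in those patients. Section 2.7.1 hopes to spot a signal worth following up, and with about 30 recipients each missing result counts.

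**Working it through.** **1. Timing of the only unconditional post-dose test.** Cycle 1 lasts 28 days and later cycles 21 days (Section 5.1). Cycle 3 Day 1 = 1 + 28 + 21 = study Day 50, the first day of week 8. The last CYT107 dose is on Day 22, and 50 − 22 = 28 days. This reproduces the week 8 and one-month figures in Section 5.

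**2. Who is covered.**

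| Patient | Cycle 3 Day 1 sample | Later sample |
|---|---|---|
| Reaches Day 50, positive | Yes | Yes (visit stated two ways) |
| Reaches Day 50, negative | Yes | No |
| Leaves before Day 50 | No | No; the condition cannot be met |

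The biopsy footnote (j) to the same calendar table has an early-exit fallback: Cycle 4 Day 1 or End of Treatment, whichever comes first. Footnote m has none.

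**3. Planned number exposed.** 6 run-in patients plus half of 48 randomized 1:1 (Section 13.3): 6 + 24 = 30. Replaced run-in patients would add to this.

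**4. Coverage.** The documents give no early-discontinuation rate, so let d be an assumed share leaving before Day 50. Expected coverage is 30(1 − d):

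| d | Covered, of 30 |
|---|---|
| 5% | 28.5 |
| 10% | 27 |
| 20% | 24 |
| 30% | 21 |

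**5. Bias.** Let s and l be the antibody-positive shares among those who stay and those who leave. The true share is (1 − d)s + d·l.

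- Rate among tested patients: bias = s − [(1 − d)s + d·l] = d(s − l).
- All treated as denominator, untested counted as negative: bias = (1 − d)s − [(1 − d)s + d·l] = −d·l.

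The documents give neither s nor l. Selected results, in percentage points, on assumed values:

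| d | s | l | Tested only | All treated |
|---|---|---|---|---|
| 5% | 10% | 10% | 0 | −0.5 |
| 5% | 10% | 30% | −1 | −1.5 |
| 20% | 20% | 40% | −4 | −8 |
| 30% | 20% | 60% | −12 | −18 |
| 5% | 20% | 10% | +0.5 | −0.5 |
| 30% | 20% | 10% | +3 | −3 |

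The tested-only rate can be low, unbiased or high, depending on whether leavers have more, equal or less antibody than stayers. The all-treated rate with untested counted as negative can only be low or correct. So can the count of positives, assay error aside, also because a patient negative at Day 50 is never retested.

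**6. How many leavers could not be sampled anyway.** Section 2.4 quotes a median survival of 7.9 months on atezolizumab. If survival were exponential, the share dying by Day 50 would be 1 − 0.5^((50/30.4375)/7.9) = 13.4%, or about 4 of 30. This is only an illustration. Section 3.1.6 requires a life expectancy of at least 12 weeks, which may make the true figure lower.

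**The case against.** **Section 9.3.1.1 may already cover leavers.** It mentions a draw at end of treatment with no condition, and Section 2.7.1 speaks of testing after the last CYT107 dose with no week limit. That is fair evidence that the intent may have been wider. But 9.3.1.1 is general collection wording, much like that used for other blood assays in Section 9, while the specific rules in 9.3.1 and footnote m are both conditional. A site working from the calendar would not draw the sample.

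**A reader might infer that measured immunogenicity is biased low.** The documents do not support that for the rate among tested patients. It needs leavers to have a higher antibody rate than stayers, and no data on this are given. The background points partly the other way. Section 2.2.2.3 reports: "One true anaphylactic reaction and 4 acute allergic reactions have been reported, strictly in studies with repeated cycles of CYT107". It also says antibodies are more frequent after multiple cycles, and this trial gives one. Patients with mild allergic reactions are not removed by the grade 3 or 4 rule and can reach Cycle 3 Day 1. Many early leavers may leave because of disease.

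**A reader might also infer that early leavers have no post-dose blood at all.** That is wrong. Plasma for kynurenine, tryptophan and arginine is due at Cycle 2 Day 1 and End of Treatment and, like the antibody plasma, is frozen at −80°C. What is missing is a scheduled antibody sample; the documents do not say that the other plasma may be used for one.

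**The stakes are limited.** Immunogenicity is an exploratory objective (Section 1.3), Section 2.7.1 says numbers are too small for firm conclusions, and nothing in Section 13 depends on antibody results. This stands, and it sets the severity.

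**Conclusion.** The gap is real and follows from the text alone: anyone leaving before Day 50 has no scheduled post-dose antibody sample, although all recipients are meant to be tested. Results will be incomplete and may be understated. The understatement is clear for the count of positives and for any rate that treats untested patients as negative; for the rate among tested patients its direction is unknown. Coverage of about 28.5 to 21 of 30 rests on assumed early loss of 5% to 30%, and not all of that loss is recoverable.

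Separately, the late sample is described in three ways: at End of Treatment if positive, at end of study if positive, and at end of treatment unconditionally. These must be reconciled. The study-end wording is the least workable: Section 5.6 ends the active study when the last patient reaches 2 years and allows telephone follow-up, so a draw may not happen. It would go too far to say that persistence of antibodies could not then be assessed, because in-person visits are also allowed and a late sample still carries information.

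Severity is minor.

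**What to change.** In footnote m, Section 5 and Section 9.3.1, state that any CYT107-treated patient without a Cycle 3 Day 1 sample has an antibody sample at the End of Treatment visit or, preferably, the 30-day Safety Follow-up, with time since the last CYT107 dose recorded. The preference is strongest for Cycle 1 leavers: a patient stopping on Day 22 reaches that visit about 30 days after the last dose, close to the planned 28. For a Cycle 2 leaver, End of Treatment may be nearer: stopping on Day 43 gives 43 − 22 = 21 days at End of Treatment, against about 51 at Safety Follow-up.

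Name one visit for the repeat in positive patients, and align Sections 9.3.1 and 9.3.1.1 with the calendar. Report antibody results among treated patients with any post-dose sample, and give the number untested with reasons.

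The cost is wording in three places plus one plasma aliquot for each early leaver who attends, at visits where safety blood is already drawn. The downside is that time since last dose and number of doses received will be less uniform across samples, so both should be shown with the results.
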